IRB-Approved Study Protocol for

Pilot validation of an app to estimate and manage portion size: The PortionSize Smartphone App

ClinicalTrials.gov ID Number: NCT04494971

Institutional Review Board Pennington Biomedical IRB FWA 00006218

Approval Date: 24 August 2020

Study Title: Pilot validation of an app to estimate and manage portion size: The PortionSize

Smartphone App

Protocol Version Date: 8/6/2020

IRB Review Plan

Objectives

Long-term Goals and Specific Objectives

Our *long-term goal* is to create simple and accessible interventions that assist individuals with weight control. In particular, we aim to provide easy-to-use phone apps that allow participants to monitor the portion sizes of the foods they consume. These apps guide participants on appropriate portion sizes and provide recommendations of food groups that should be consumed. To that end, we have developed the PortionSize app. This app measures portion sizes and enables users to quantify energy composition of foods consumed, further to the amount of food groups consumed, including food supplements. Moreover, the app provides personalized, real-time rudimentary feedback on portions consumed based on an individual's current weight and weight goals. For instance, individuals with a given weight looking to gain or lose weight will be encouraged by the app to increase and decrease the amount of portions they consume, respectively. We foresee the app being utilized in the obesity field to help people understand how large their portions are and to help them manage (reduce) portion size and better adhere to a weight loss diet. We also think that the app has other potential uses, including treatment of patients with anorexia nervosa, and to help improve nutrition intake. However, we must first validate the app to ascertain if it provides a valid and reliable measure of portion size, and if it is convenient and usable.

Specific objectives:

(1) Examine the validity, reliability and perceived participant satisfaction of the PortionSize app.

Background

We propose to improve the accuracy of portion size measurement, as it is poorly determined by self-report measures [1]. This will occur via the development of the **PortionSize smartphone app**. This app will provide templates superimposed on individuals food images to provide real-time visual feedback of food consumed. We will validate the ability of PortionSize to measure portion size, energy/macronutrient intake and food groups. Specifically, we will first compare measures calculated from the app against weighed portions of food groups and rater analysis of food photos in a controlled setting and then deploy the app in free-living conditions to examine the validity against rater analysis of food photos. We will also assess satisfaction and general convenience of the app with users.

The study will yield a convenient, easy-to-use app ready to calculate portion size and food intake measurement. It will also pave the way for further validation work, and ultimately provide an app that assists individuals in managing their portion sizes, nutrition, and body weight.

Page 1 of 8 Version 3: 8/6/2020

Rationale and Significance

Overweight and obesity are a burgeoning public health concern, yet only a small minority of smartphone apps that claim to facilitate healthy eating and weight loss incorporate evidence-based principles [2]. Such innovations are important as humans fundamentally cannot accurately estimate portion size. Indeed, portion size estimation errors account for ~50% of the error in self-reported food intake [1], and data from our laboratory has demonstrated that extensive training results in only modest improvements in portion size estimation accuracy and that portion size estimates remain inaccurate [3]. Another study found that professionals with extensive nutrition training (i.e. Licensed Registered Dietician Nutritionists) cannot accurately estimate portion size [4]. These data clearly indicate that there is a significant need for an app that allows users to obtain real-time feedback about the portion size of their food selections, and our research indicates that no existing app fulfills this need. Obtaining apps that accurately quantify portion sizes would be incorporated into existing or future weight loss interventions, as well as treatments that foster adherence to diabetic diets or other special diets (e.g., diets to reduce hypertension, triglyceride or enhance intake with).

Inclusion and Exclusion Criteria Inclusion Criteria are:

- 1. Aged 18-65
- 2. Male or female age 18-65 years
- 3. BMI 18.5-45 kg/m² based upon self-reported height and weight
- 4. Have an iPhone and an operable Apple ID, password, and email address and is willing to use these to collect data during the study, acknowledging that data usage, and associated charges, are a result of study participation

Exclusion Criteria are:

- 1. For females, pregnancy or breast feeding
- 2. Currently diagnosed with an eating disorder
- 3. Disease that severely affects metabolism, including diabetes, hypercholesterolemia, or dyslipidemia.
- 4. Has gained or lost more than 10 lbs in last 3 months
- 5. PBRC Faculty/Staff Member
- 6. Has suffered serious mental illness that has resulted in serious functional impairment and has substantially interfered with one's life activities within the last 5 years.
- 7. Any other medical, psychiatric, or behavioral factors in the judgement of the Principle Investigator or Medical Investigator that may interfere with study participation or the ability to follow the protocol

Number of Subjects

We expect up to 15 participants to complete both Phase 1 and Phase 2. Pennington Biomedical Research Center employees are not eligible to participate.

Page 2 of 8 Version 3: 8/6/2020

Recruitment Methods

A sample of up to 15 adults will be recruited from the Baton Rouge, Louisiana area to participate in both Phase 1 and Phase 2.

Study Timelines

Participants will complete the procedures as noted in the Procedures section. The study involves one visit to Louisiana State University (LSU) campus or the Pennington Biomedical (PBRC) campus for Phase 1. Phase 2 will be completed in-person or remotely after Phase 1 before participants make a return visit to either LSU or PBRC afterwards.

It will take up to six months to recruit participants and have them complete Phase 1 and Phase 2. All data analyses and study cessation will occur shortly after.

Study Endpoints

The primary endpoint of this study is validity and reliability of portion size and energy intake measurement, measured with the PortionSize app in controlled and free-living conditions.

Secondary endpoints include satisfaction with the PortionSize app and the ease of using the app.

Procedures Involved

Phase 1: Testing the PortionSize Smartphone App. The validity, reliability and satisfaction of the PortionSize app under controlled conditions will be quantified in the Phase 1. Participants will partake in an in-person lab visit at either LSU or PBRC. All assessments will be conducted in a controlled room. Initially, participants will complete an informed consent. Then participants will have their height and weight recorded and will complete a set of questionnaires on demographics and lifestyle factors. A food frequency questionnaire (Diet History Questionnaire, Version 3.0 [5]) will also be administered. Afterwards, participants will be trained on using the PortionSize app.

Next, participants will use the app to measure the portions, energy composition and the food groups of pre-weighed foods that differ in size and composition. These food items will be provided by the researchers and will serve as the criterion measures of portion size, energy content and food group quantity, further to rater analysis of food photos [6]. Food portions administered will be carefully selected to reflect a plethora of food items and portion sizes. Some selected food items will be reassessed within and between users to obtain intra- and inter-rater reliability, respectively. The participant will not consume the food items they are administered to assess.

Participants will complete a user preference survey (Appendix 1: PortionSize User Preference Survey (Phase 1)) to report their satisfaction with the PortionSize app. This survey evaluates how much participants liked the app and includes questions about ease of use and satisfaction. The survey was modeled from surveys developed to assess satisfaction with the Remote Food Photography Method app [6]. Afterwards, the participants will complete the Computer System Usability Survey (CSUQ) [7].

Page 3 of 8 Version 3: 8/6/2020

Phase 2: Testing the PortionSize Smartphone App in free-living conditions

Phase 2 will occur in participants' natural environment and will involve the 15 participants from Phase 1. In free-living conditions, participants will capture before and after pictures of the foods and food supplements they consume and use the app to quantify the portion sizes of the items within the pictures. Participants will use the app for 3 days (two weekdays and one weekend day) in free-living conditions.

At the end of Phase 2, we will compare the portion size, energy/macronutrient composition and food group data collected from PortionSize and compare these to rater analysis of food photos. Participants will also return to complete the same CSUQ survey on app usability. Lastly, the PortionSize User Satisfaction Survey (Phase 2) (Appendix 2) will be administered to assess participant satisfaction and the ease of using PortionSize app for capturing information about portion sizes.

Description	Phase 1	Phase 2
Consent and eligibility	x	
Remote training on the use of app to capture food images and quantify portion sizes	X	
Lifestyle and Demographics Questionnaire, RFPM Lifestyle Interview, Food Frequency Questionnaire, body weight, height, BMI	X	
Use of app to measure pre-weighed lab meal portions	X	
Pen and paper User Satisfaction Surveys	х	
Instructed to use app over 3-day period in free-living setting		х
Return for pen and paper User Surveys		x

All named personnel have experience with the IRB approval process and field experiment designs.

Data and Specimen Management

Analysis

Phase 1 analysis objectives include:

- 1) Determining if portion size estimation measured with the PortionSize app is significantly different from criterion values (directly weighed food portions).
- 2) Determining if energy, macronutrient, saturated fat, added sugar and food group estimation measured with the PortionSize app is significantly different from criterion values (directly weighed food portions and rater analysis of food photos).
- 3) Determining how reliable the PortionSize app is in examining energy, macronutrient, saturated fat, added sugar and food group values.
- 4) Determining the differences in energy, macronutrient, saturated fat, added sugar and food group values between rater analysis of the food photos and directly weighed foods.
- 5) Determining the differences in estimated energy, macronutrient, saturated fat, added sugar and food group error between the PortionSize app and the rater analysis of food photos.
- 6) Determining if the PortionSize app provides a reliable measure of portion size, energy intake, macronutrient intake, saturated fat, added sugar and food groups.
- 7) Determining if participants are satisfied with the PortionSize app as measured in Appendix 1 (PortionSize User Preference Survey (Phase 1)).
- 8) Determining if the PortionSize app is easy to use and provides adequate instructions for use.
- 9) Qualitative assessments by respondents of the desirable and undesirable features of the app.

Phase 2 analysis objectives include:

- 1) Determining if portion size estimation measured with the PortionSize app in free-living conditions is significantly different from the criterion value (rater analysis of food photos).
- 2) Determining energy, macronutrient, saturated fat, added sugar and food group estimation measured with the PortionSize app in free-living conditions is significantly different from the criterion value (rater analysis of individual food photos).
- 3) Determining if energy intake estimation measured with the PortionSize app in free-living conditions is significantly different from estimated energy requirements [8-10].
- 4) Determining if energy intake estimation measured from the rater analysis of food photos is significantly different from estimated energy requirements [8-10].
- 5) Quantifying satisfaction levels with the PortionSize app as measured in Appendix 2 (PortionSize User Preference Survey (Phase 2)).
- 6) Qualitative assessments by respondents of the desirable and undesirable features of the app.

Withdrawal of Subjects

Subjects may be withdrawn from the study if they are non-compliant with study procedures and they will be notified of their withdrawal via telephone or mail.

Subjects may voluntarily withdraw from the study at any time. No additional data will be collected and they will be considered drop outs in the study.

Page 5 of 8 Version 3: 8/6/2020

Risks to Subjects

This study involves no greater than minimal risk. The main risk is breach of confidentiality, and the PBRC team will work to minimize this during data collection, handling, and analysis.

Potential Benefits to Subjects

Participants may benefit by increased awareness of their portion sizes with various food groups.

Setting

All research procedures will be conducted at LSU main campus, PBRC's campus, or remotely through videoconference calling, and in participants' natural environment.

Resources Available

PBRC and LSU main campus has all the necessary equipment needed to undertake and execute the proposed research project successfully. All investigators and staff have offices or cubicles. Investigator offices are each equipped with a desk, chair, filing cabinets and shelves, telephone with voice mail, and access to a printer, photocopier and fax. Computers are equipped with software for statistics, data management, and word processing, and computers are connected to the PBRC mainframe with internet access and email access through Outlook Express. Information Technology (IT) provides full technical support to all members of the faculty and staff. PBRC has all the technological equipment and staff needed to conduct the present study. These information technologies assure efficient data handling and optimal communication among the investigators and the team.

Compensation

Participants will be compensated \$75 for successful completion of both Phase 1 and Phase 2. All compensation and recruitment success figures are based on historical averages from previous PBRC studies with similar respondent burden.

Confidentiality and Provisions to Protect the Privacy Interests of Subjects

Participants' records will be kept confidential to the extent allowed by law. Only Drs. [name], [name], and [name], and the PBRC research team will have access to the information participants provide. We will use an identification number rather than participants' names on study records. The information participants provide will be stored on secured network drives and will not be identified using any personal information.

Participants' names and other facts that might identify them will not appear when we present this study or publish its results. The findings will be summarized and reported in group form. Participants will not be identified personally. All participants will have ample opportunity during consent and throughout the study to ask questions concerning study procedures. These questions will be answered promptly and fully by study staff to ensure participant ease. A participant may choose not to answer questions or participate in study procedures at any time.

Data Safety Monitoring Plan

Study recruitment, study progress, participant complaints, data collection, data management, data integrity, data security, and eventually data analysis will be staffed at weekly meetings at PBRC.

Page 6 of 8 Version 3: 8/6/2020

Compensation for Research-Related Injury

No form of compensation for medical treatment or for other damages (i.e., lost wages, time lost from work, etc.) is available from the Pennington Biomedical Research Center or LSU. In the unlikely event of injury or medical illness resulting from the research, the participant will be referred to a treatment facility. Medical treatment may be provided at their expense or at the expense of their health care insurer (e.g., Medicare, Medicaid, Blue Cross-Blue Shield, Dental Insurer, etc.) which may or may not provide coverage. PBRC is a research facility and provides medical treatment only as part of research protocols. Should the participant require ongoing medical treatments, they must be provided by community physicians and hospitals.

Economic Burden to Subjects

There will be no study related costs to the participant. However, use of the PortionSize app will use data from the participant's cellular data plan. Hence, it is possible that the participant would incur cost for this data and this is clearly disclosed in the consent form.

Consent Process

All subjects participating in the study will provide written informed consent. The consenting process will take place in private rooms at Pennington Biomedical Research Center or LSU main campus and will be conducted according to Pennington Biomedical consenting guidelines and practices. Participants can take the consent form home to review prior to deciding if they wish to enroll. All participants are free to withdraw from the study at any time.

Page 7 of 8 Version 3: 8/6/2020

References

- 5 Diet History Questionnaire, Version 3.0. National Institutes of Health, Applied Research Program, National Cancer Institute. 2018.

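### Validity is part of the primary endpoint, but the app-versus-criterion objectives ask only for a significant difference; the plan does not commit to reporting bias or limits of agreement

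*Combined protocol and SAP*

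**What the plan says.** Study Endpoints: "The primary endpoint of this study is validity and reliability of portion size and energy intake measurement", in controlled and free-living conditions. The Objectives section gives the purpose: "we must first validate the app to ascertain if it provides a valid and reliable measure of portion size". Procedures Involved adds for the laboratory phase: "The validity, reliability and satisfaction of the PortionSize app under controlled conditions will be quantified in the Phase 1". The Background says of the study: "It will also pave the way for further validation work".

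The Analysis section is a list of objectives. Four of them compare the app with its criterion:

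- Phase 1 objective 1, portion size: "Determining if portion size estimation measured with the PortionSize app is significantly different from criterion values (directly weighed food portions").
- Phase 1 objective 2, energy, nutrients and food groups: "significantly different from criterion values (directly weighed food portions and rater analysis of food photos").
- Phase 2 objectives 1 and 2: the same two questions in free-living use, with photo ratings as the criterion.

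Phase 2 objective 3 sets app energy intake against estimated energy requirements in the same terms. No section names a test, a significance level, a confidence interval, limits of agreement or a unit of analysis.

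The data are repeated within person. In Phase 1, "Food portions administered will be carefully selected to reflect a plethora of food items and portion sizes". In Phase 2, "Participants will use the app for 3 days (two weekdays and one weekend day) in free-living conditions". Number of Subjects gives up to 15 people for both phases.

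**The concern.** A test of difference asks whether the average error can be told apart from zero. Validity of a measuring tool asks two other things: how large the average error is, and how far a single reading may lie from the truth. If the objectives are followed as written, a significant result shows that there is bias but not whether it matters. A non-significant result may reflect only few participants or noisy readings. Neither result describes error in the individual reading, which is what a user of the app meets.

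At stake is what the pilot hands on. Later validation work needs the bias and the spread of error, for design and for judging whether the app is worth pursuing. A list of significant and non-significant comparisons can rank apps the wrong way round.

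**Working it through.** **Inputs.** From the documents: up to 15 participants. The plan gives no power calculation or precision target, so it has no figure to reproduce. Assumed, because the documents are silent: a paired t-test on one app-minus-criterion difference per participant, two-sided 0.05, and an SD of the differences of 5% to 35% of the criterion value.

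**1. What the test can detect.** With non-centrality (bias/SD) × √n and n - 1 degrees of freedom, 80% power at n = 15 needs bias = 0.78 SD. That is 7.8% at SD 10% and 0.778 × 35 = 27.2% at SD 35%. With 12 completers it is 0.89 SD.

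**2. Chance that a true 10% bias is non-significant.**

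| SD of differences | n = 15 | n = 12 |
|---|---|---|
| 10% | 5% | 12% |
| 15% | 33% | 44% |
| 20% | 56% | 65% |
| 25% | 70% | 76% |
| 35% | 82% | 85% |

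The assumed SD decides the answer. Averaging over foods also matters. With 15 foods per person and residual SD 30%, the SD of a person's mean is √(participant SD² + 30²/15). This gives 9.2%, 12.6% and 21.4% at participant SD 5%, 10% and 20%, and the chance of non-significance becomes 3%, 19% and 61%.

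**3. Two apps compared, n = 15.** Limits of agreement are bias ± 1.96 SD.

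- App A, bias 0 and SD 20%: limits 0 ± 39.2%. Non-significant 95% of the time, by construction of the test.
- App B, bias 5% and SD 5%: limits 5 ± 9.8, that is -4.8% to +14.8%. Here bias/SD = 1, and the test is significant 95% of the time.

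A reader guided by the test would usually prefer A, although B's readings lie far closer to the criterion. This does not arise from the small sample: with more data A still passes 95% of the time, and B fails even more often.

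**4. Level of analysis.** With an assumed participant SD of 20% and residual SD of 30%, limits for a single food are ±1.96 × √(20² + 30²) = ±70.7%. For one person's mean over 15 foods they are ±1.96 × √(20² + 30²/15) = ±42.0%. A limit of agreement means little unless its level is stated.

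**5. Precision of the proposed analysis.** One value per participant, t(0.975, 14) = 2.145:

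- Bias: half-width 2.145/√15 = 0.55 SD (0.64 SD at n = 12).
- Each limit: half-width 2.145 × √(1/15 + 1.96²/28) = 0.97 SD (1.12 SD at n = 12).

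These do not apply to an item-level analysis. A simulation with 15 people and 15 foods (participant SD 10-20%, food SD 0-20%, residual SD 30%) gave about 0.3 to 0.5 of the total SD for each limit. The documents give neither the number of foods nor any variance component, so this is an illustration only.

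**The case against.** The strongest reply has four parts.

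- **The lists are not closed.** They say what the objectives include, no test is named, and a paired test is itself computed from the mean difference and its SD, so both would be to hand. This is right as far as it goes. It would be wrong to say that the plan excludes agreement analyses or that a difference test yields no information on bias or spread. What stands is that no section commits to reporting or interpreting those quantities for a primary endpoint.
- **Spread is partly covered.** Some Phase 1 items are reassessed within and between users, and objectives 3 and 6 concern reliability. For a weighed item the criterion is fixed, so variation between users is variation in error. That stands for the reassessed items. It does not show agreement with the criterion, since an app can be consistently wrong, and it does not reach Phase 2.
- **Error is addressed in Phase 1 objective 5.** That objective compares app error with photo-rater error. It leaves out portion size, does not define error and has no Phase 2 counterpart. The app could match the raters and still be inaccurate.
- **It is a small, minimal-risk pilot.** True, and this favours estimation over testing. It also means that the lack of a preset acceptable-error margin should not be counted as a fault.

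A reader might also infer that the sponsor means to read non-significance as proof of validity, or to analyse repeated foods as independent observations. The documents say neither.

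**Conclusion.** The concern holds as a gap in the primary validity analysis that should be fixed. The text is clear: all four app-versus-criterion objectives pose a difference question, and none commits to the size of the bias or the limits of individual error. The ranking problem in step 3 follows from the nature of the test. Its figures, and the 0.78 SD detectable bias, assume one value per participant, n = 15 and two-sided 0.05; every SD is an assumption. The claim that non-significance would be weak evidence is therefore conditional: for a 10% bias it ranges from a 5% to an 82% chance of a miss at n = 15 over SD 10% to 35%. The point that a difference test cannot establish agreement does not depend on those SDs.

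**What to change.** In the Analysis section:

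1. For Phase 1 objectives 1 and 2 and Phase 2 objectives 1 and 2, make the main validity analysis the mean app-minus-criterion difference with 95% CI, plus Bland-Altman limits of agreement with CIs. Allow for repeated foods and days within participant, for example by a mixed model with a participant effect, and a food effect in Phase 1.
2. State the level of each analysis: the food item for portion size; the day total for Phase 2 energy and nutrients; for Phase 1 energy and nutrients, either the food item or a total that the sponsor defines, counting each reassessed item once. The documents do not define a Phase 1 meal total.
3. For Phase 2 objective 3, report the mean difference with 95% CI.
4. State that a non-significant difference will not be read as validity. An acceptable-error margin, fixed before the data are seen, is optional for this pilot.

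The cost is a little more analysis work, repeated over the listed nutrients and food groups; no new data and no larger sample. Intervals will be wide. With one value per participant at n = 15 and SD 10-35%, half-widths are about 5.5 to 19 percentage points for the bias and 10 to 34 for each limit. That is acceptable for a pilot that feeds further validation.

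### Free-living portion size is judged only against photo raters, and no listed Phase 1 objective checks those raters against weighed food for portion size

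*Combined protocol and SAP*

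**What the plan says.** Study Endpoints defines the primary endpoint as "validity and reliability of portion size and energy intake measurement, measured with the PortionSize app in controlled and free-living conditions". Portion size outside the laboratory is therefore a primary measure.

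The Background undertakes to "validate the ability of PortionSize to measure portion size, energy/macronutrient intake and food groups" in two steps. The first is to "compare measures calculated from the app against weighed portions of food groups and rater analysis of food photos in a controlled setting". The second is to "deploy the app in free-living conditions to examine the validity against rater analysis of food photos". Phase 2 objective 1 in the Analysis section matches the second step: the criterion for portion size is the photo rating alone.

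Under Procedures Involved, Phase 1, the pre-weighed foods "will serve as the criterion measures of portion size, energy content and food group quantity, further to rater analysis of food photos". In the Analysis section, Phase 1 objective 1 compares app portion size with weighed portions and does not name raters. Objective 4 covers the "differences in energy, macronutrient, saturated fat, added sugar and food group values between rater analysis of the food photos and directly weighed foods". Objective 5 compares app error with rater error for the same outcomes. Neither lists portion size.

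**The concern.** In free living nothing is weighed, so the photo rater stands in for the truth. A difference between app and rater mixes the errors of both, and a small difference can arise because both are wrong in the same direction. Phase 1 is the only place where the rater can be set against the scale. For energy, the other primary measure, that check is listed. For portion size, the measure the app is named for, it is not.

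At stake is how a favourable Phase 2 result can be read. If app and raters agree on portion size, the analyses as listed give no direct figure for how far the raters themselves are from weighed amounts.

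**Working it through.** The plan gives no figure to reproduce here, so the main check is a tabulation of the listed objectives by outcome and by the pair of measures compared.

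| Comparison | Portion size | Energy |
|---|---|---|
| App vs weighed food (Phase 1) | Objective 1 | Objective 2 |
| App vs rater (Phase 1) | none listed | Objective 2 |
| Rater vs weighed food (Phase 1) | none listed | Objective 4 |
| App error vs rater error (Phase 1) | none listed | Objective 5 |
| App vs rater (Phase 2) | Objective 1 | Objective 2 |
| App vs estimated requirement (Phase 2) | not applicable | Objective 3 |
| Rater vs estimated requirement (Phase 2) | not applicable | Objective 4 |

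Phase 1 objective 6 also names portion size, but it concerns the reliability of the app and not the accuracy of the raters.

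**Why agreement alone is ambiguous.** App − rater = (app − truth) − (rater − truth). If app and raters were both 10% low (an assumed value), the relative difference would be 0.90/0.90 − 1 = 0.

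**Whether rater error could be derived anyway.** If app, rater and scale values exist for the same foods, mean rater error follows by subtraction: (app − weighed) − (app − rater) = rater − weighed. With assumed values of 100 units weighed, 85 from the app and 90 from the rater: (85 − 100) − (85 − 90) = −15 + 5 = −10, which equals 90 − 100. This needs rater portion sizes for the Phase 1 photos. No section says whether they are recorded there, or in what unit.

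**Indirect evidence from objective 4.** If the rater identifies the food correctly and applies a fixed energy density d, the relative energy error is (d × rated amount)/(d × weighed amount) − 1, which equals the relative error in amount. Under that condition the energy comparison is informative about amount. The documents do not say how raters derive energy.

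**What a lab figure could and could not do.** Take an assumed app bias of −20% and rater bias of −10%. The observed Phase 2 difference is 0.80/0.90 − 1 = −11.1%. Working back, app bias = (1 + observed) × (1 + rater bias) − 1:

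- free-living rater bias −15%: 0.889 × 0.85 − 1 = −24.4%
- free-living rater bias −10%: 0.889 × 0.90 − 1 = −20.0%
- free-living rater bias −5%: 0.889 × 0.95 − 1 = −15.6%

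The same Phase 2 result fits quite different app biases, depending on whether lab rater error carries over. The lab estimate helps interpretation but does not separate the two errors.

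No precision is calculated for the added estimate. The documents give no SD and no number of foods, photos or raters, so any half-width would rest wholly on assumed inputs.

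**The case against.** The strongest reply is that the plan largely covers this already. The Background and the Phase 1 procedures name raters alongside weighed food in the controlled setting, and the natural reading of the procedures makes them a second criterion for portion size. The objectives are introduced as a non-exhaustive list. The list also looks loosely drafted: objective 3 addresses reliability without portion size, and objective 6 repeats reliability with portion size added. The omission from objectives 4 and 5 may therefore be no decision at all. Objective 4 informs on amount through energy, macronutrients and food groups, and objective 1 tests the app directly against the scale in the same participants.

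Most of this stands, and it limits the weight of the point. It also rules out two stronger readings. A reader might infer that the plan excludes any check of raters on portion size; the documents do not support that, because the comparison is only unlisted. A reader might also infer that raters go unchecked altogether; objective 4 contradicts that.

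The reply does not supply the comparison itself. Objective 1 names weighed food only, energy and food-group values are not the portion-size endpoint, and nothing confirms that raters record portion size in Phase 1. A criterion for a primary measure should not depend on inference from the procedures text.

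**Conclusion.** The point holds as a minor improvement. As listed, the only criterion for free-living portion size is not itself compared with weighed food on portion size, whereas the criterion for energy is compared with weighed food on energy. This rests on the text of the objectives and needs no numerical assumption. The biases used in the illustrations are assumed, and the documents do not allow rater error to be sized.

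It would go too far to conclude that the Phase 2 portion-size result is uninterpretable, or that the missing comparison would put it right. The result remains a measure of agreement with raters, with indirect support from Phase 1. The added estimate would come from foods that are not eaten in the lab, while Phase 2 concerns what participants consume in their own surroundings.

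**What to change.** - Add portion size, in the unit used for Phase 1 objective 1, to Phase 1 objectives 4 and 5.
- State that raters record portion size for the Phase 1 photos. Phase 2 objective 1 already requires a rater value for portion size, so the task is not new to them.
- Report mean rater-minus-weighed bias with a 95% CI, by rater if there are only one or two. The procedures say "Some selected food items will be reassessed within and between users", so foods may recur across participants; state whether the interval refers to the foods and raters actually used or to a wider population.
- Describe Phase 2 objective 1 as agreement with raters, read it beside the Phase 1 estimate, and say that the estimate is a consistency check and not a correction.

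The cost is a few analysis lines on foods already weighed and photos already planned for rating, plus possibly some extra recording by raters. The estimate will be imprecise in a pilot of this size ("We expect up to 15 participants to complete both Phase 1 and Phase 2"), and lab error may not carry over to free living. Both limits should be stated with the result.
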